B] Allocation concealment mechanism:

The supervisor of the study will write the randomization numbers of the patients in opaque white papers folded three times to form sealed envelopes and store it inside a box. Then will keep the Codes for randomization at the secretary office.

C] Implementation:

At time of intervention, the main operator will send the patient to the secretary office. Then, the assigned employee will open the box and ask the patient to select one envelope. the main operator will assign each participant for the

corresponding intervention either (friction or frictionless group) according to the list of codes of randomization.

Assignment to either intervention will occur before leveling and alignment stage.

D] Blinding:

Blinding of the operators: Blinding will not be possible for the operators during the application interventions and during the follow up visits. The principal operator is responsible for assigning subjects to interventions according to the concealed allocation, appliance activation at follow up visits, dental impressions and acquisition of dental casts.

Blinding of the outcome assessors: It is a single blinded study, the outcome assessors only will be blind. The patients name will be sealed from pre and post study models. Then two assessors will carry on, blindly and independently, the measurements and analysis of the study.

III) Data collection, management and analysis:

A] Data collection methods:

Primary outcome:

1. Retraction rate: to assess the antero-posterior movement of anterior teeth and first molars, the principle investigator will take study models for every participant monthly during the follow up visits. Then will digitize the models and identify the landmarks, reference lines and planes on the pre, interim and post-retraction digital dental models for measurements reading.

Secondary outcomes:

- 1. Anchorage loss:*** will be accessed by the principal investigator via scanned study models before and after the completion of retraction by identifying the landmarks, reference lines and planes, then will interpret the measurements in degrees and millimeters.
- 2. Pain:*** Each patient will fill a questionnaire regarding his treatment experience in a VAS scoring from 1-10. The questionnaire will include several questions related to oral hygiene, pain and discomfort experienced throughout the trial.

B] Data management:

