A colleague outside the research team will enter the data and organize it in excel sheets in the computer of the orthodontic department.

Data will include all photographs, models, radiographs and filled questionnaire.

C] Statistical Analysis:

- The principle investigator will be responsible for the extraction of the required data from the study models taken at every follow up visit. The data will be sent to a specialized statistician.
- The specialized statistician will be responsible for the statistical analysis of the study by:
 1. Presenting the data as mean, standard deviation (SD) and Standard error (SE) values.
 2. Using Paired t-test to compare between the friction and the frictionless group of retraction as well as to compare between the pre-and post -treatment data for each group.
 3. Using Kolmogorov Smirnov and Shapiro Wilk tests to determine the rate of anterior segment retraction.

4. Statistically evaluate the patient acceptance for both techniques.

- For this study, the specialized statistician will use IBM11 SPSS12 Statistics Version 20 for Windows to perform the required statistics.
- The significance level will be $P \leq 0.05$. Highly significant variables are detected when P value is less than 0.01.

Assessors Reliability:

- To achieve high reliability for measurements, the supervisor will choose a well-experienced inter-examiner during the study.
- A training session will be provided for the examiners to ensure standard measurements techniques.
- Each examiner will complete the measurements on a model and will repeat the procedure after one week to assess the intra- and inter-examiner reliability.
- The supervisor will compare the measurements of the two assessors for disagreement with a difference of more than one millimeter.
- The supervisor will evaluate the amount of variation in measurements among and between examiners to test the performance of each assessor.
- The examiner with less reliability will receive additional training but will be replaced during the study.
- The specialized statistician will calibrate the intra and inter-examiner reliability for the measurements of the study by Inter-observer and intra-observer reliability was assessed using $P \leq 0.05$.

IV) Method Monitoring:

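### Examiner reliability is judged by a P value, which does not measure agreement; the only numeric check (1 mm) is coarse for anchorage loss, and it is unclear whose readings are analysed

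*Combined protocol and SAP*

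**What the plan says.** The Assessors Reliability list, under III) C] Statistical Analysis, contains these elements:

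- A training session for the examiners.
- A repeat measurement: "Each examiner will complete the measurements on a model and will repeat the procedure after one week". How many models this covers is not stated.
- A numeric check: "The supervisor will compare the measurements of the two assessors for disagreement with a difference of more than one millimeter". What follows when the difference is larger is not stated.
- A review by the supervisor of variation within and between examiners, with no statistic or limit.
- A consequence: "The examiner with less reliability will receive additional training but will be replaced during the study". As worded, this cannot be applied.
- A statistical criterion: "Inter-observer and intra-observer reliability was assessed using" P ≤ 0.05. The sentence is broken and names no statistic.

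On who measures, the plan says two things. II) D] Blinding says: "Then two assessors will carry on, blindly and independently, the measurements and analysis of the study". No rule combines the two readings. III) A] Data collection methods says that "the principle investigator will take study models for every participant monthly during the follow up visits", and has the same person digitise the models and identify the landmarks. It says that anchorage loss "will be accessed by the principal investigator via scanned study models before and after the completion of retraction". C] Statistical Analysis adds: "The principle investigator will be responsible for the extraction of the required data from the study models taken at every follow up visit".

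**The concern.** Retraction and anchorage loss are both read off scanned models by placing landmarks, so reading error goes straight into the outcome data. A reliability check should show how large that error is in mm and whether it is acceptable. A P value shows neither. As a difference test, it is insensitive to random error. As a test of a coefficient against zero, it can be passed with poor agreement.

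Anchorage loss is the more exposed outcome, because mini-screws are used to keep it small. Error that is large relative to it costs precision and could hide a difference between the arms.

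Whose readings count matters for a different reason. The principal investigator takes the models at follow-up visits, when the appliance is in the mouth, and so could know the arm. If that person's readings were analysed, error could differ by arm, and averaging over patients would not remove it.

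**Working it through.** The plan states no reliability figure, reading error, sample size or SD for anchorage loss, so there is nothing to reproduce. Inputs marked *assumed* are not in the documents.

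**1. The P value as a difference test.** Take 20 models (*assumed*), a constant 0.2 mm offset between assessors (*assumed*) and reading SD s per assessor. The paired difference has SD s√2, so the noncentrality is 0.2 / (s√2/√20), with 19 df.

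| s (mm) | noncentrality | chance of P ≤ 0.05 |
|---|---|---|
| 0.1 | 6.32 | >99% |
| 0.2 | 3.16 | 85% |
| 0.3 | 2.11 | 52% |
| 1.0 | 0.63 | 9% |

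The noisier the assessors, the more often the test finds no difference.

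**2. The P value as a test of a coefficient.** For a one-way ICC with two raters and 20 models, the critical F on 19 and 20 df is 2.137 (one-sided) or 2.482 (two-sided). With ICC = (F − 1)/(F + 1), this gives 1.137/3.137 = 0.36 or 1.482/3.482 = 0.43. A Pearson correlation of 0.444 is likewise significant with 20 models. Values this low would pass.

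**3. The 1 mm trigger.** Literature Review section 4 quotes mini-screw anchorage losses of 0.88 mm (upper molars, against 2.07 mm with headgear) and 0.2 mm in each arch (against 2.0 and 2.1 mm with conventional anchorage). A third study saw none. The trigger is 1/0.88 = 1.14 and 1/0.2 = 5 times the two mm figures. With no offset, the share of reading pairs flagged is 2Φ(−1/(s√2)): about 0%, 0.04% and 1.8% at s = 0.1, 0.2 and 0.3 mm (*assumed*).

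**4. Cost to anchorage loss.** A change between two models carries error variance 2s² with one assessor and s² with the mean of two. For a true between-patient SD q of 1.0 to 0.5 mm (*assumed*), the variance is multiplied as follows.

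| s (mm) | one assessor, 1 + 2s²/q² | mean of two, 1 + s²/q² |
|---|---|---|
| 0.1 | 1.02–1.08 | 1.01–1.04 |
| 0.2 | 1.08–1.32 | 1.04–1.16 |
| 0.3 | 1.18–1.72 | 1.09–1.36 |

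**5. The primary rate.** D] Outcomes defines all outcomes as the T0 to Tfinal difference. Over m months the rate has error variance 2s²/m². At s = 0.3 mm and m = 6 (*assumed*) this is 0.18/36 = 0.005 (mm/month)². A mean of equal-interval monthly increments telescopes to the same quantity, because the interim readings cancel. A least-squares slope through the seven models has 0.09/28 = 0.0032. A single-month increment has 0.18, which is 36 times the T0 to Tfinal value.

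**6. Whose readings.** Blinding gives the measurements to two blinded assessors. Data collection gives landmark identification and anchorage loss to the principal investigator, and Statistical Analysis gives that person the data extraction. No sentence ranks one above the other.

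**The case against.** Several counter-arguments are sound and limit the point.

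- **The 1 mm contrast is not like for like.** The trigger applies to one pair of readings, whereas 0.2 and 0.88 mm are group means, and random error averages over patients. A reader might infer that the plan accepts errors up to 1 mm. It does not say so; the figure only prompts a comparison. What stands is that no tighter check in mm exists for anchorage loss.
- **The quoted losses may not transfer.** Under Clinical Procedure, screws are placed in the upper arch only. The two arms also load the anchorage differently: the chain runs to the screws, while the T-loop is cinched behind the second molars with the screws tied to the canines.
- **Monthly models do not by themselves threaten the primary outcome.** A reader might infer a two- to threefold rise in rate variance by setting monthly error against the canine-rate SDs quoted in the literature review (0.46 and 0.34 mm/month). That would apply only to single-month increments, which the plan does not say it analyses. Those SDs are also observed values that already contain measurement error.
- **A constant assessor offset cancels** in a change score when one assessor reads both models. Step 1 shows how the criterion behaves, not bias in the outcome.
- **It is easy to choose an unfavourable reading SD.** At 1/(1.96√2) = 0.36 mm the trigger flags 5% of pairs by construction, which is no evidence that error is that large.
- **Other safeguards exist:** training, a repeat reading, supervisor review and retraining. They have no statistic or limit, but they are not absent. The broken sentence may have lost a named statistic; if so, the plan still needs to state it.

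A reader might also conclude that outcome assessment is unblinded. The documents do not support that. They provide for two blinded assessors and elsewhere assign the same work to the principal investigator, so this is an unresolved conflict.

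**Conclusion.** The point holds in limited form. The stated reliability criterion cannot show agreement on either reading of the sentence, and this conclusion needs no assumed figure. The 1 mm check is too coarse to reassure about anchorage loss, and the remaining checks have no limit.

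The cost in precision depends on unknown inputs: the variance factors of 1.02 to 1.72 (one assessor) and 1.01 to 1.36 (mean of two) rest entirely on the assumed SDs. At the low end the effect is negligible. Loss of power cannot be computed without a sample size and an anchorage-loss SD. The effect on the primary rate is small for a T0 to Tfinal rate, a mean monthly rate or a slope, and large only for single-month increments.

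The conflict over whose readings are analysed is certain from the text. Whether it leads to biased readings is not. The change is worth making because the two blinded assessors are already planned.

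**What to change.** 1. Delete P ≤ 0.05 as the reliability criterion. Report an absolute-agreement ICC with 95% CI and the method-error SD in mm, within and between examiners, separately for retraction and anchorage loss.
2. State the number of coded models, drawn from both arms, that each assessor re-measures after one week. Twenty, as used above, is only an illustration.
3. Set in advance a re-read trigger in mm, below 1 mm for anchorage loss and justified against the loss expected in this trial. Pairs beyond it are re-read blind.
4. Analyse the mean of the two blinded assessors' readings. Reconcile Blinding, Data collection methods and Statistical Analysis so that these readings, not the principal investigator's, supply the outcome data.
5. State whether the rate is taken from T0 to Tfinal or from monthly readings, and reword the retrain-or-replace sentence so that it can be applied.

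Cost: changes to the text, some repeat and re-read measurements, and coding of the interim models if they are analysed, since names are to be sealed only on the pre and post models. No extra patients, visits or assessors are needed.
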